CCHMC IRB Protocol 2011-2045 was a pilot study including 15 neonates demonstrating safety and feasibility of the NICU MRI. Photographs from the scanning process and images from the first patients are attached in Appendix F. Permission to use the photographs was obtained from the parents of the baby.

Subsequently we have scanned nearly 600 patients on the NICU MRI without adverse event under CCHMC IRB Protocol 2011-2850.

STUDY METHODS:

This is a study to use a customized MRI system installed in the CCHMC NICU to perform medically indicated MRI exams in the neonatal population.

Study population:

Neonates admitted to CCHMC for whom an MRI exam is medically indicated will be recruited into the study. All neonates in the study will be viable, as defined in subpart B of the Code of Federal Regulations. The infants will be medically stable to undergo the MRI procedure, as determined by the attending neonatologist.

Study design:

Infants who may meet study criteria will be identified by the attending neonatologist and study staff will be notified of a potential candidate for the study. As per usual clinical care, orders for the MRI will be placed in EPIC.

Inclusion criteria:

- Any infant admitted to CCHMC
- Have a medical condition for which an MRI exam is indicated, as determined by the attending neonatologist

Exclusion criteria:

- Infants too large to fit in the customized NICU MRI system comfortably (generally infants > 6 kg)
- Standard MRI exclusion criteria as set forth by the CCHMC Division of Radiology

Pre-scan:

The attending neonatologist will determine whether the MRI scan is to be done with sedation or without sedation. Whenever possible, infants will be scanned without sedation utilizing a feed and bundle technique. Occasionally, at the discretion of the

neonatologist, sedation will be necessary to obtain the imaging required for clinical diagnosis. This mirrors the process utilized on the conventional magnets in the Department of Radiology. The use of sedation and/or contrast is not part of the research.

Prior to MRI scanning, the patient's NICU care team will attempt to contact parent/LAR to communicate that a MRI has been ordered and provide information on the device, any potential risks and answer any questions the parent/LAR may have.

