Infants will be prepared for the MRI exam at the bedside by switching all monitoring devices over to MRI compatible monitors. Switching monitoring devices confers no additional risk to the patient. Hearing protection will be used for acoustic noise reduction. Infants will then be moved to the MRI control room and transferred to the patient table/transfer station by the NICU nurse and/or physician.

Standard MRI safety screening will be performed by the MRI technologist per Department of Radiology practice. Screening will be documented according to standard Department of Radiology procedure.

MRI scan:

All studies will be performed with a nurse and/or physician in the control room. The specific MR sequences used will be determined by the type of exam to be performed based on the medical indication. Some patients may get IV contrast and/or sedation if indicated by the specific MR exam protocol. The scanner will be operated by a certified MR technologist.

Sequences will be obtained using the OPTIMA electronics during each MRI exam in order to have images from a device that is FDA cleared. Additional sequences will be obtained with the HDX/GE platform. Images from the HDX/GE platform are expected to be of diagnostic quality equal to or better than those obtained from an adult-sized 1.5T MRI scanner. If the patient remains stable throughout the MRI exam, an additional 10 minutes of scanning beyond the clinically indicated sequences may be obtained for ongoing sequence development and improvement efforts.

All coils used will be FDA cleared. Those not cleared will be submitted to the IRB and approved before they are used.

Monitoring of safety and tolerability:

Adverse events will be monitored during the MRI scan by the MRI technologist and the nurse/physician in the control room. Only adverse events that take place during MRI scanning will be recorded. Adverse events will be recorded on an adverse event log form kept in the MRI control room. In the event of an adverse event, the study team will be notified and a full report of the specific event will be submitted to the IRB promptly. Nurses will collect vital signs for clinical care purposes, but there will be no vital sign collection as part of this protocol.

6

Evaluation of MRI data:

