As is done for any medically indicated clinical MRI exam, all images acquired will be interpreted by a board certified pediatric radiologist or neuroradiologist and a standard report will be generated. This report will be included in the neonate's medical record and made available to the clinical team. The MRI data collected using the OPTIMA/HDX MRI platform will be used in conjunction with the images obtained using the FDA cleared OPTIMA MRI platform and the results of other appropriate standard diagnostic tests to inform diagnosis and/or subsequent medical management. Deidentified images may be used in publications or in support of a 510K application to the FDA.

Sample size:

The goal of this study is to make MRI available to all neonates admitted to CCHMC for whom an MRI exam is medically indicated. Thus, the maximum number of patients recruited into the study per year will reflect the maximum number of patients admitted into the NICU. A review of the historical data documenting the number of patients admitted to the CCHMC NICU over a five year period (2006 – 2010) indicated that on average, 714 (range 662-759) patients were admitted each year over that period.

DURATION:

This protocol is considered a continued access protocol and will remain open indefinitely.

POTENTIAL BENEFITS:

By eliminating the need to transfer neonates from the NICU to the main Radiology Department for an MRI exam, neonatal patients will benefit by avoiding the medical risk associated with removal from the NICU. Patients evaluated on the NICU MRI will also benefit from reduced acoustic noise, lower RF power deposition and less chance of peripheral nerve stimulation during the MR exam as compared to that associated with exams performed on the adult sized conventional MR scanner. Patients may also benefit from earlier and/or more comprehensive and accurate diagnosis and medical management.

POTENTIAL RISKS, DISCOMFORTS, AND INCONVENIENCES:

MRI exams are considered minimal risk for research purposes. The customized NICU MRI scanner will have no increase in risk beyond conventional adult MRI scanners. Although chart review is not part of this protocol, there is a risk of loss of confidentiality

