of medical record information related to maintenance of research records. In order to protect the privacy of medical information, the research records will be coded and access to the records will be limited to research personnel. The MR report will be included in the clinical medical record to supplement diagnosis and medical management. All other study specific data (e.g. parental permission, safety record) will be de-identified and kept in a locked cabinet. No individual identifiers will be used in publications or reports resulting from the study. After the study is completed and the results are published, the records will be destroyed.

RISK/BENEFIT ANALYSIS:

In the opinion of the investigators, this study involves no increase over minimal risk with potential immediate and direct benefit to the study subjects and potential benefit to future patients and the scientific community. We believe that making MRI more readily available to this population will benefit their subsequent medical management. In addition, infants in the study may, in fact, have less risk than they would during an MRI scan obtained on a conventional clinical MRI system as part of usual clinical care, due to the decreased risk of acoustic noise injury and the elimination of the risk associated with transporting the infant out of the NICU to the Radiology department.

SECURITY/CONFIDENTIALITY:

All subjects enrolled in this study will be identified in research records by a unique study number only. The MR report will be included in the clinical medical record to supplement diagnosis and medical management. All other study specific data will be deidentified. Protected health information will be entered into a secure database. A single copy of a list linking medical record number to study number will be kept locked and available only to study investigators. All records will be kept in a locked cabinet at CCHMC and maintained by the study investigator. All computerized records will be password protected.

REIMBURSEMENT/PAYMENT FOR STUDIES:

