The parents/LARs of the study patient and/or their medical insurance company will be responsible for the financial charges/costs associated with each of the MRI exams he/she receives using the OPTIMA NICU MRI platform while enrolled in the study as these are examinations being performed for clinical indications. These costs will be identical to those incurred by patients who receive MRI exams on the adult sized conventional MRI scanners in the main Radiology Department. The costs associated with additional imaging performed using the OPTIMA/HDX NICU MRI platform will be assumed by

the Department of Radiology. There will be no compensation or payment to the study participant.

RECRUITMENT:

Patients will be identified based on clinical need. After potential study subjects are identified, the NICU fellow or attending assigned to the patient (the fellow and attending are also part of the study team) will discuss the study with the parents/ LARs.

Informational flyers or materials directed at healthcare providers and/or the general public may be created. All marketing materials will be approved by the IRB prior to circulation.

CONSENT:

We are requesting a Waiver of Documentation of Informed Consent in accordance with 45 CFR 46.117 and 21CFR56.109 for this study. According to these regulations, the IRB may waive the requirements for investigators to obtain signed consent if one of two requirements are met. Our research study meets the second criterion that "the research presents no more than minimal risk of harm to subjects and involves no procedures for which written consent is normally required outside of the research context (45 CFR 46,117)".

MR imaging is of no more than minimal risk for patients and is performed daily for clinical care of children in the CCHMC system. Other than potential administration of intravenous contrast (utilized only when clinically indicated), there is no instrumentation of, or intervention on, the patient as part of the MRI exam. Accordingly, specific procedural consent is not signed by LARs for the performance of MRI on conventional scanners (or administration of intravenous contrast) as part of normal clinical care.

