The fellow or attending taking care of patient will call the parents/LARs and introduces him/her self. The fellow or attending then verifies that they are speaking with the correct parent/LAR using information. The physician will tell the parent/LAR that their child is scheduled to have an MRI of their brain/spine/abdomen/etc. and explain why the MRI is needed. Next, they tell them that they are calling the get their permission to use our NICU MRI. The script that follows will be used after the above introduction:

"An MRI machine uses a computer and a big magnet to take pictures. The magnet in our NICU scanner is much smaller than the magnets used in the MRI machines downstairs in the Radiology department. We are one of the only NICU's in the country that have MRI capability within the NICU as opposed to the hospital-wide radiology suite. Our MRI machine uses a smaller magnet than a typical MRI machine. Individually the MRI magnet and imaging software are FDA approved, but together as one unit they are not, therefore, I need your permission to use our NICU MRI for your child's study. We use the same process for obtaining the study and are able to get the same quality images using this machine as we would if your child were to have their MRI done in radiology, but with the added benefit of not having to travel off the unit. There are no additional risks by using the NICU MRI and in general we find it safer and more seamless to obtain the images when not having to travel off the floor. The same Radiologists read these images and we are able to bill your baby's insurance. There are no additional costs beyond the costs of an MRI in the big scanner downstairs. We will collect basic information about your child and the type of scan that was performed as part of quality control for the study. There are no known risks to the MRI scan itself and the MRI does not involve radiation. If you do not wish to have your baby's MRI performed in the NICU, we will schedule your baby to move downstairs for the MRI- sometimes it takes a little longer to schedule that. Do you have any questions for me at this time? ... Do you consent to having your baby's scan being done in our custom- built NICU MRI?"

A participant information sheet will be provided to parents/LARs. This information sheet serves as a study summary.

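### The verbal consent script says the MRI scan itself has no known risks, while the protocol names a reduced, not absent, risk of acoustic noise injury from scanning

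*Protocol*

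**What the plan says.** The script in the CONSENT section, used by the NICU fellow or attending to obtain unsigned consent, contains the sentence "There are no known risks to the MRI scan itself and the MRI does not involve radiation". A little earlier, and separately, it tells parents that using the NICU scanner brings no additional risk.

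Other sections of the protocol describe the hazards of scanning differently:

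- RISK/BENEFIT ANALYSIS argues that infants may be at less risk than on a conventional scanner, partly "due to the decreased risk of acoustic noise injury" and partly because transport out of the unit is avoided.
- POTENTIAL BENEFITS lists "reduced acoustic noise, lower RF power deposition and less chance of peripheral nerve stimulation" compared with the adult-sized scanner.
- STUDY METHODS, Pre-scan, states: "Hearing protection will be used for acoustic noise reduction".
- STUDY METHODS, Monitoring of safety and tolerability, states: "Adverse events will be monitored during the MRI scan by the MRI technologist and the nurse/physician in the control room".

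**The concern.** A statement that no risk is known is absolute. One named risk of the scan, anywhere in the same protocol, is enough to contradict it. The protocol names such a risk, and it uses the reduction in that risk as part of its case for the NICU scanner. The investigators therefore count less noise injury as a benefit in one section, and in another have parents told that there is no known risk to reduce.

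What is at stake is the accuracy of what parents hear. The script is operative text: consent is verbal, parents often have to be reached by phone, and for families who do not speak English the interpreter reads the script itself. The protocol is meant to stay open indefinitely, so the sentence would go on being used.

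**Working it through.** The protocol gives no figure for this point. The check sets its statements side by side.

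**1. What the script sentence covers.** It speaks of the scan itself, not of a difference between scanners. The comparative message is given in its own sentence. Reading the disputed sentence as a second comparison would make it redundant and would ignore its wording.

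**2. Whether the protocol names a risk of the scan itself.** RISK/BENEFIT ANALYSIS gives two reasons for lower risk, noise injury and transport, so the noise risk belongs to scanning and not to the journey. The two reasons are also worded differently within one sentence. The transport risk is said to be eliminated; the noise risk is only "due to the decreased risk of acoustic noise injury". The authors thus distinguish a risk removed from a risk reduced, and place noise injury in the second group.

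**3. Whether other hazards are named.** POTENTIAL BENEFITS speaks of "reduced acoustic noise, lower RF power deposition and less chance of peripheral nerve stimulation". Noise and radiofrequency power are exposures; nerve stimulation is an effect on the infant. All three are described as lower or less likely, none as absent. PREVIOUS WORK IN THIS AREA lists specific absorption rate, acoustic noise and peripheral nerve stimulation among the topics of the system's safety testing.

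**4. Precautions.** Hearing protection and adverse-event monitoring during the scan fit a recognised hazard. They do not prove one, and the conclusion does not rest on them.

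**5. Whether the safety record rescues the sentence.** The protocol reports nearly 600 patients scanned without an adverse event. Taking n = 600 as an assumption, the one-sided 95% upper bound p on the event probability solves (1 − p)^n = 0.05:

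p = 1 − 0.05^(1/600) = 0.0050, or about 0.5%.

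Zero events is reassuring and compatible with a low risk. It does not show that no risk is known, and RISK/BENEFIT ANALYSIS still names the noise injury risk in a protocol that reports this experience.

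**Result.** Step 2 alone contradicts the sentence. Step 3 adds to it. Steps 4 and 5 do not change it.

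**The case against.** The strongest case against the point is that the tension comes down to very little text. The noise injury phrase is comparative, two of the three items in POTENTIAL BENEFITS are exposures and not harms, and hearing protection is only a precaution. The decision parents face is between the NICU scanner and the one in Radiology, and the sentence bearing on that choice, that no risk is added, agrees with the rest of the protocol. A physician gives the explanation, and is present to answer questions when an interpreter is used. All of this stands as a limit on the consequence. It does not make the absolute sentence true, because one named risk suffices.

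A reader might also infer stronger conclusions that the document does not support:

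- **That the minimal-risk classification contradicts the script.** The protocol says "MRI exams are considered minimal risk for research purposes" and, in arguing for the waiver of signed consent, "MR imaging is of no more than minimal risk for patients". This is a regulatory category, in the second case worded as a ceiling. A ceiling is compatible with no known risk, so this wording is no part of the contradiction.
- **That the team breaks its own disclosure commitments.** Under Pre-scan the care team is to "provide information on the device, any potential risks and answer any questions", and CONSENT also promises an explanation of possible adverse reactions. The script names none, but it is used together with an information sheet that is not shown, and the commitments are not confined to the script. A failure to disclose cannot be established. Equally, a complete sheet could not make the spoken sentence true; it would disagree with it.
- **That the number of families measures the harm.** The prior protocol's yearly averages of consents and the historical NICU admissions show how many people might be involved. They say nothing about the effect of the sentence on any decision.
- **That the 10 extra minutes of scanning for sequence development are concealed.** Whether parents are told of them is a separate question, which again depends on the unseen sheet.

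**Conclusion.** The point holds in a narrow form. The absolute statement in the script is contradicted by RISK/BENEFIT ANALYSIS, which names a reduced risk of noise injury, and by POTENTIAL BENEFITS, which treats radiofrequency deposition and nerve stimulation as lower or less likely. This rests only on the protocol's own words and needs no assumption about the information sheet.

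The size is small. No endpoint, analysis or clinical procedure is affected. The scan is medically indicated wherever it is done, the sentence applies to MRI on either scanner, and by the protocol's account the unmentioned exposures are lower on the NICU scanner, so leaving them out does not favour the study device. Any effect on parents' decisions cannot be derived from the document.

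A reader might go on to infer that the consent process is invalid or that the waiver argument fails. Neither follows: the waiver rests on risk being no more than minimal, and a small named risk is consistent with that.

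**What to change.** In the verbal script, delete the clause that says no risk of the scan is known and keep the remark that MRI does not involve radiation. In place of the deleted clause, put a short, non-comparative statement built from what the protocol already says. For example: MRI is considered minimal risk; the scan exposes the baby to noise, for which hearing protection is used, and to radiofrequency energy; and there is a small chance of nerve stimulation. The protocol text gives no size for that chance, so the word small should be checked against the safety testing data in Appendix E.

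Add no statement that these exposures are lower on the NICU scanner. That would put a claim favouring the device into the consent script, and it would sit badly with the CONSENT section, which says that possible adverse reactions do not differ from those on conventional scanners. Reconcile the new wording with POTENTIAL BENEFITS, POTENTIAL RISKS, RISK/BENEFIT ANALYSIS, that statement in CONSENT, and the information sheet, so that parents hear and read the same thing.

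The cost is a short wording amendment with IRB approval, a check of the sheet, and a script that is slightly longer and slightly less reassuring.

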APPENDIX A: OPTIMA 430s data sheets and operating manual.

APPENDIX B: HDX/GE data sheets and operating manual.

APPENDIX C: Detailed description of 1) modifications made to the MR systems to accommodate whole body MRI of the neonate; 2) patient table developed to accommodate the smaller size of the magnet.

